**Principal Investigator: [name]**

**Phase II: The BREATHE intervention**

## **STUDY PURPOSE AND RATIONALE**

### **Study Purpose**

The **overall goal** of this study is to develop and to preliminarily validate a novel intervention delivered by primary care providers (PCPs) to their Black adult patients with uncontrolled asthma in federally qualified health centers (FQHCs). We recently developed and rigorously tested a brief questionnaire, the Conventional and Alternative Management for Asthma (CAM-A) tool, that screens patients for beliefs about asthma self-care and inhaled corticosteroid (ICS) treatment and prompts PCPs to discuss ICS adherence at office visits based on patient CAM-A responses. In over 300 adults (80% Black; 67% uninsured or government-insured) with high rates of uncontrolled asthma (69%), the validated CAM-A identified that erroneous personal health beliefs and negative ICS beliefs were commonly endorsed (93% and 68%, respectively). Importantly, erroneous personal health beliefs were significantly associated with uncontrolled asthma, likely driven by ICS non-adherence. In the first phase of this trial we held six focus groups (AAR0605) with adult asthma patients and their loved ones to inform the intervention by adapting an evidence-based brief shared decision-making strategy with proven efficacy, delivered by PCPs, for use with our validated CAM-A tool. As such, this project has three **specific aims**:

### **Specific Aims:**

- 1. To develop an intervention to improve asthma control in Black adults receiving care in FQHCs (completed);**
- 2. To evaluate the feasibility and acceptability of the intervention procedures; and**
- 3. To assess the preliminary evidence of intervention effects on asthma control (primary outcome), ICS adherence, forced expiratory volume in one second (FEV1) – an objective lung function measure – and asthma quality of life (secondary outcomes) over a 3-month follow-up period.**

**Please note, we already have IRB approval for Phase I (focus group and PCP review only). Focus groups are completed and independent PCP review is about to begin (AAR0605).**

**In this application we are seeking approval of Aims #2 and #3 (Phase II-pilot intervention).**

### **Background / Rationale**

**Uncontrolled asthma due to ICS non-adherence is common among Black adults.** Nearly every asthma-related hospitalization and death could be prevented with appropriate self-management that achieves and maintains disease control. However, as many as 64% of adults have uncontrolled asthma; minorities are disproportionately represented within that population. While inhaled corticosteroids (ICS) are a safe and effective treatment for uncontrolled asthma, relative to Whites, Blacks have lower rates of ICS adherence (74% vs. 29%).

**Health beliefs are associated with ICS non-adherence.** Erroneous personal beliefs about asthma and its pharmacologic treatment are among the most significant factors contributing to ICS non-adherence. ICS non-adherence, a primary cause of uncontrolled and/or fatal asthma, is more common in Blacks relative to Whites due, in part, to higher rates of endorsement of non-pharmacologic approaches to asthma self-care (e.g., coffee is a safe, effective asthma treatment) and negative ICS beliefs (e.g., ICS is addicting)

These beliefs have been shown to be associated with ICS non-adherence, more asthma attacks and delays in seeking care.

**There are unique challenges to achieving asthma control in FQHCs.** PCPs deliver up to 80% of asthma care. However, compared to specialists, uncontrolled asthma is more common in their patients. There are unique challenges to achieving asthma control in FQHCs, a particular type of primary care setting designated to receive enhanced Medicaid reimbursement because their clientele are underserved, underinsured, and uninsured Americans who receive more episodic primary care. In these settings PCPs have limited time to evaluate asthma control, to assess ICS non-adherence, and to identify beliefs associated with ICS non-adherence. This speaks to the pressing need for novel brief interventions that facilitate evidence-based guideline-directed asthma self-management.

**Shared decision-making interventions to promote asthma control in this vulnerable population are lacking.** The study is guided by the theoretical model of Shared Decision-Making in evidence-based practice, which posits that the best treatment decisions are informed by patient's preferences, the best available evidence, and practitioner expertise. The PCPs role is to facilitate discussion of the risks and merits associated with specific options in the context of patients' goals and preferences, and in a manner that activates patients to engage in self-management. PCPs offer options to consider jointly with the goal of reconciling differences and reaching mutually agreed upon higher quality decisions that align patients' needs with evidence-based guideline-directed care. Prior research has demonstrated that with repeated lengthy engagement (1+ hour), highly-trained interventionists in settings other than primary care can increase medication adherence; this intervention model improves disease control, identifies health beliefs that conflict with evidence-based care and reduces risky behaviors. The framework's application to asthma has been limited to children and to White privately insured adults. Sustained implementation of effective shared decision-making interventions has been restricted, in part, by burdensome protocols requiring multiple visits, lengthy engagement, highly-trained interventionists, and by protocols inappropriate for populations like those served in FQHCs.

**Implementation research is underutilized in asthma intervention research.** Evidence-based interventions may be difficult to sustain, in part, because factors associated with implementation are overlooked. To close this gap between research and practice, researchers should conduct formative assessments with the target audience and program providers during development, and evaluate the program features that enhance a program's reach. Further, FQHCs are overlooked in asthma intervention research.

**Impact.** Black adults with uncontrolled asthma experience profound health disparities. Despite data that point to the critical need for enhanced asthma self-management, we continue to see rates of controlled asthma well below Healthy People 2020 targets, particularly among vulnerable populations. Our **Brief Evaluation of Asthma Therapy (BREATHE)** intervention has the potential to offer a new avenue to asthma control via shared decision-making that supports ICS adherence.

## STUDY DESIGN AND PROCEDURES

This R21 proposal will proceed in two major phases: (1) a development phase (Year 1) where **BREATHE** was developed using iterative community-based participatory research (CBPR) approaches with feedback from PCPs (focus groups completed; independent PCP review about to commence); and (2) a pilot randomized trial phase that will allow estimation of parameters crucial for a larger randomized control trial (RCT) including final content specification, participant recruitment rates, and potential intervention effect sizes (the focus of this application).

## PHASE II ONLY

### Study Procedures

#### Pilot Randomized Clinical Trial Phase

**Study Procedures: PCP Recruitment, Consent and Randomization.** Randomization will be at the level of the PCP. This is a two-group randomized trial with outcomes analyzed at the patient level. We will randomize 8 PCPs (4 / FQHC site) into **BREATHE** and attention control conditions stratified for provider type (physician vs. nurse practitioners [NPs]/physician assistant [PAs]) to insure equal numbers of PCPs within each PCP type are assigned to each condition. Randomization lists will be computer generated in advance by our data manager (allowing the biostatistician to remain blinded during analysis). We do not anticipate difficulty in recruiting 4 PCPs/FQHC since one FQHC has ~15 PCPs (10 physicians and 5 NPs/PAs) and the other has 35 (20 physicians and 10 NPs/PAs).

**Provider Consent.** After reading the informed consent and having questions addressed, PCPs will be asked to sign informed consent indicating they are entering the study voluntarily. Declinations to enroll, if any occur, will be a metric that we will track. Consent will be obtained by either the PI or the Project Manager as these individuals are unblended.

**Inclusion Criteria:** PCPs (MDs and NPs/PAs) working in family, primary or internal medicine care services who have at least 40 adult patients with persistent asthma (defined as having been prescribed ICS) on their patient panel will be considered eligible for enrollment.

**Exclusion Criteria:** PCPs whose primary focus is outside of adult health services (family, primary or internal medicine), such as behavioral health, pediatrics and OB-GYN.

**Patient Recruitment.** We will recruit patients using methods we have used successfully in prior studies. The FQHC administrator will create a potential list of subjects using a combination of ICD-10 (Asthma 493)-specific queries of electronic membership records and searching of scheduled patient visits for the FQHC PCPs to review. The research team will receive only the names and contact information of those the FQHC clinicians have contacted and who agree to receive a call from the research team. We will also accept subjects who respond to posted recruitment flyers.

**Patient Participants & Consent.** We will enroll 80 Black adults with uncontrolled asthma (10 / PCP). The study team will read the informed consent and when subjects have had all questions addressed, they will be asked to sign indicating they are entering the study voluntarily. Consent will be obtained the RA who is blinded.

**Inclusion Criteria:** Patients must be 1) adults ( $\geq 18$  years of age) who self-report race as Black or African American; 2) with PCP-diagnosed persistent asthma; 3) prescribed ICS; 4) receiving asthma care at participating FQHCs; 5) who have uncontrolled asthma (defined below) ; and 6) have erroneous personal health and/or negative ICS beliefs (defined below).

Interested participants who meet the first 4 criteria will be screened for uncontrolled asthma by administering the Asthma Control Questionnaire (ACQ) by phone (phone administration is both reliable and valid). The ACQ includes 6 self-reported items about asthma symptoms and an objective measure of pulmonary function:

the forced expiratory volume in one second (FEV1). The ACQ has demonstrated validity and reliability with and without the use of the FEV1. ACQ scores  $\geq 1.5$  have a positive predictive value of 88% in identifying uncontrolled asthma in clinical trials. PCPs will be notified of all patients with ACQ scores  $\geq 1.5$  and patients will be scheduled for a follow-up visit with their PCP as these scores indicate that asthma is not in good control. At that visit, if they remain interested in enrolling in the trial, they will be screened for beliefs associated with ICS non-adherence using the CAM-A instrument, administered on customized tablet that allows for immediate scoring. patients will complete the 17-item CAM-A which will self-score. Any one endorsement of a non-prescription asthma management preference or negative ICS belief is considered a positive screen and the patient is eligible for enrollment in this two-step screening process (+ ACQ screen by phone and + CAM-A screen at visit). At this visit, trained study staff will also obtain the FEV1 using a hand held spirometer calibrated daily, as well as additional surveys (see Table 1).

**Exclusion Criteria:** 1) participation in Phase 1 of the **BREATHE** trial (focus groups); 2) non-English speaking; 3) serious mental health conditions (e.g., psychosis) that preclude completion of study procedures or confound analyses.

**Enrollment feasibility.** The two FQHCs provide primary care to over 100,000 unique patients a year, who are cared for by 50 providers. Each provider sees approximately 2,000 asthma patients. Using a conservative estimate of 8% asthma prevalence, 160 unique patients with asthma are served per provider. Based on our preliminary studies we expect ~69% of subjects screened will have uncontrolled asthma (n=110 patients / PCP); of these, 97% will screen positive on the CAM-A yielding 107 eligible patients / PCP. Thus, we have an adequate patient pool from which to draw 10 patient subjects / PCP.

**Blinding.** Patient codes, tied to PCP assignment (active vs. control), will be entered into a tablet prior to the completion of the CAM-A by the RA. The meaning of these codes will not be known to the RA. Using these codes, the software will trigger the tablet to load either the **BREATHE** intervention steps or the attention control timer (described below) after the CAM-A has been completed. These screens will be hidden from the patient and the RA by two “hold” screens warning the RA/patient subject not to advance further. We will assess the adequacy of blinding of the subject and the RA as a process outcome at the end of the study. Both active and control PCPs will receive the tablet from the RA and the results of the lung function testing (FEV1). The RA will set up two digital recorders to capture the audio of the office visit and then leave the room. The RA will be instructed to stay close by to monitor the end of visit but not close enough to overhear the conversation. The statistician ([name]) will be blinded. The PI, Project Manager and database manager will not be blinded.

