**Step 4: Shared decision-making (2 minutes).** The PCP and patient jointly consider treatment options. The PCP will actively attempt to build consensus around ICS adherence, reconciling conflicts to better align beliefs with evidence-based guideline-directed ICS treatment. For example, if the patient uses ICS intermittently (rather than the required twice-daily dosing) because of an erroneous belief that tolerance to ICS develops with daily dosing, then the PCP will attempt to counter that belief using responses gleaned from the CBPR development phase (focus groups) and information from national guidelines. This will likely include encouraging the patient to use ICS once a day (50% adherence) as an initial short-term plan to be followed by a return visit and re-evaluation of asthma control. If the patient declines to engage in shared decision-making or declines attempts at negotiating ICS use, then the PCP and the patient agree to disagree. This is a one-time intervention.

**Usual care with an attention control condition.** Patient codes associated with PCPs randomized to the attention control condition will trigger the tablet to load a 7-minute timer for the PCP to use to track the length of the attention control condition (discussion of healthy lifestyles). Control PCPs will have access to all the data that the active intervention PCPs have: the ACQ score, CAM-A results, and lung function results. To control for contact, they will be instructed to engage in a 7-minute diet and exercise discussion as this will not confound results and it was a common topic in our prior study; ICS adherence was not discussed.

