**Intervention Training for BREATHE PCPs.** We will train PCPs randomized to the **BREATHE** condition using procedures we have used before with content gleaned from our CBPR development phase (focus groups and PCP review) as described previously. The core training for PCPs delivering the **BREATHE** intervention will be conducted by our consultant, [name], and will consist of one, 2-hour instructional session: 30 minutes of didactic instruction addressing the delivery of the 4 steps of the brief intervention; 10 minutes of role-playing of commonly encountered scenarios and; a 50 minute skills workshop in which PCPs role play creating a trusting environment, relinquishing sole decision-making, motivating and empowering patients to engage in self-management decisions. A question and answer period will conclude the training. PCPs will receive a laminated action card that fits in a lab coat pocket summarizing the intervention steps as a resource although the steps of the intervention will be available to the PCP on a tablet during the visit.

Immediately after training, PCPs will be tested using a standardized patient scenario to demonstrate that he/she can deliver the intervention in 7 minutes or less. All testing will be audiotaped and a trained rater will determine

whether the critical elements of the brief intervention were completed in 7 minutes using the validated Brief Negotiation Interventions Adherence Scale (BAS) adapted to asthma (see draft BNI protocol and BAS). If the PCP fails testing, she/he will receive additional instruction and retested. Prior studies have shown that such remediation re-training results in 100% proficiency. PCPs will be encouraged to informally try out some of these techniques before the study goes live. The Consultant will follow-up with each PCP to answer questions from this “dry run” before the first subject is enrolled.

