Recruitment. We will recruit patients using methods we have used successfully in prior studies. The federally-qualified health center (FQHC) administrator will create a potential list of subjects using a combination of ICD-10 (Asthma 493)-

specific queries of the electronic membership records and searching of scheduled patient visits for the FQHC PCPs to review. The research team will receive only the names and contact information of those the PCP permits the team to contact. We will also accept subjects who respond to posted recruitment flyers.

**Informed Consent.** The study team will read the informed consent and HIPAA to the subject and will discuss it section by section. When subjects have had all questions and concerns addressed, they will be asked to sign the consent indicating they are entering into the study voluntarily. Participants will be given a copy of the HIPAA and the signed informed consent document; a copy of the informed consent and HIPAA will be maintained with the study team.

**Auditing Selected Cases.** Fidelity to consenting, data collection and the intervention will be evaluated in the following manner. Twenty percent of all visits will be randomly selected for auditing of the informed consent and data collection protocols. In addition, intervention fidelity will be assessed by reviewing audiotapes of 20% of randomly selected visits (with the exception of the first visit; all first visits be reviewed) to be rated by three independent blinded raters. At least one additional file per PCP will be reviewed prior to enrollment of their 5th patient subject, to evaluate drift and the length of BREATHE sessions, and length, content and contamination, if any, of control sessions. Consultant [name] will conduct additional training to enhance intervention fidelity and brevity if problems are identified.

**Minimizing research –associated risk.** While the behavioral intervention itself is a low risk intervention, participants must have uncontrolled asthma to be eligible for enrollment. Because of this, we will ask the SMC to use the established threshold for asthma exacerbations (defined below) with the team's input (see details below).

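### PCPs who may already know their arm decide which patients the team can call, and nothing requires list review and contact to be finished before allocation is disclosed

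*Combined protocol and SAP*

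**What the plan says.** All references are to the combined protocol and SAP.

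- **Unit and blinding.** Eight PCPs are randomized, and outcomes are analyzed on their patients (PCP Recruitment, Consent and Randomization). The Blinding section covers the patient, the RA and the statistician. PCPs are not among those blinded.
- **Gate to patients.** An administrator builds a list that the FQHC PCPs review. Under Patient Recruitment the team will "receive only the names and contact information of those the FQHC clinicians have contacted and who agree to receive a call". DSMP section b instead limits the team to "those the PCP permits the team to contact". Flyer respondents are accepted as well.
- **When the arm is known.** For BREATHE PCPs, "Immediately after training, PCPs will be tested using a standardized patient scenario", and the consultant follows up on a trial run of the techniques "before the first subject is enrolled". Control PCPs get no training, but "they will be instructed to engage in a 7-minute diet and exercise discussion"; the date of that instruction is not given.
- **Use of the estimate.** Aim 3 begins "To assess the preliminary evidence of intervention effects on asthma control (primary outcome", and Study Design and Procedures says the pilot should allow estimation of "potential intervention effect sizes" for a larger trial.
- **Phone ACQ6.** The Survey Administration table lets the RA or the Project Manager collect it. The text above that table gives all patient data collection to the blinded RA, and Patient data collection (Statistical Procedures) says the same of blinded RAs. The Blinding section states that the Project Manager is not blinded.

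**The concern.** When clusters are randomized and patients are recruited afterwards, randomization protects the comparison of patients only if recruitment does not depend on the arm. Here the randomized person also controls the main route by which patients reach the study. A PCP who knows the arm could, without intending to, put forward patients who seem more or less ready to change their ICS use. The arms would then differ before any intervention is delivered, and the difference would be read as part of the effect on asthma control.

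The phone ACQ6 raises a smaller, separate matter. It decides eligibility and is the only ACQ questionnaire scheduled before the intervention, so it should not be open to collection by someone who knows the allocation.

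**Working it through.** **1. Order of events**

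- Patient steps, from Patient Recruitment and Patient Participants & Consent: administrator's list, PCP review, clinician contact and agreement to a call, phone ACQ, visit with CAM-A, enrollment.
- BREATHE PCPs know their arm from training, which precedes the first enrollment.
- Control PCPs know it at the latest when the tablet loads the timer at their first study visit, and possibly earlier, when they are instructed.
- Review and contact come before enrollment. Training before the first enrollment therefore does not place training before review. It does not place review before training either, and no section fixes that order.
- Enrollment runs one patient after another within a PCP: Anticipated Problems and Strategies calls for a file review before the PCP's fifth patient. The list also draws on scheduled visits, which suggests, without proving, that patients are identified on a rolling basis. Any review or contact after a PCP's first study visit is done by someone who knows the arm.

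**2. Room for choice per PCP**

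The plan's own figure comes first. Enrollment feasibility uses 2,000 patients per provider (100,000 / 50), 8% with asthma, 69% uncontrolled and 97% CAM-A positive. The text calls the 2,000 asthma patients, but the 8% step shows that all patients are meant.

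- 2,000 x 0.08 = 160; 160 x 0.69 = 110.4; 110.4 x 0.97 = 107.1. This reproduces the plan: "yielding 107 eligible patients / PCP".
- 10 / 107.1 = 9.3%.

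The lower end uses the PCP inclusion criterion, a panel of at least 40 adults with persistent asthma, defined by an ICS prescription, with the same two rates (assumed to apply to that panel):

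- 40 x 0.69 x 0.97 = 26.8; 10 / 26.8 = 37%.

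Both pools are before race and consent, and the 107 is also before ICS prescription. Both are counts after the ACQ and CAM-A screens, whereas the PCP acts before those screens, on about 40 to 160 patients. The fractions also reflect patient agreement and the cap of 10. They bound the pool and do not measure how selective PCPs are.

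**3. Could a baseline comparison settle it afterwards?**

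Inputs from Power & Sample Size: SD 0.76, intra-cluster correlation 0.2, 10 patients per PCP, 40 per arm. They are assumed to hold at baseline, although the entry rule of ACQ 1.5 or more may lower the SD.

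- Design effect = 1 + 9 x 0.2 = 2.8.
- SE of the chance arm difference = 0.76 x sqrt((2/40) x 2.8) = 0.284.
- 95% range: 1.96 x 0.284 = 0.56 either way (normal), or 2.447 x 0.284 = 0.70 (t, 6 df).
- The planned effect is 0.5 x 0.76 = 0.38.

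Chance alone can produce a baseline difference larger than the planned effect, so a baseline ACQ comparison would not show whether selection occurred. This says nothing about the size of any selection.

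**4. Adjustment**

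Hypotheses 2 allows PCP- and patient-level confounders but names none. The RA collects CAM-A before the arm-specific screen loads, and MARS-A at Visit 1 (order within the visit not stated). Both bear on ICS beliefs and use and could serve as covariates. The Readiness Ruler, closest to motivation, is collected at Visit 1 by the unblinded provider.

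**The case against.** The strongest reply is that the point rests on silence. The sponsor may intend to finish list review first, no section gives PCPs a reason to choose differently by arm, and Patient Recruitment speaks of clinicians generally rather than each randomized PCP contacting his or her own patients. The ACQ and CAM-A thresholds limit selection on control and beliefs, a blinded RA takes consent, and flyers bypass the PCP. CAM-A and MARS-A are available for adjustment. Feasibility is the stated primary goal, and DSMP item f says the trial is not powered for significance. Front-loading review and contact would also sit awkwardly with recruitment from scheduled visits.

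Much of this stands, and it lowers the weight of the point. It does not close the gap. The thresholds do not act on motivation or expected adherence. The RA consents only those who pass the gate. Covariates that are not named, and that do not capture motivation, cannot be relied on to remove the difference. Although feasibility comes first, the plan still tests ACQ two-sided at 0.05 and means to carry the effect size forward.

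A reader might infer that PCPs will know their arm when they review the list, or that the 9% shows strong selection. The documents support neither: the order is not stated, and the fraction is not a measure of PCP choice.

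**Conclusion.** The point holds as a gap in the safeguards. Unblinded, randomized PCPs gate the main recruitment route, BREATHE PCPs are trained before the first enrollment, and nothing requires review and contact to be completed before the arm is disclosed. Followed as written, the plan permits selection to differ by arm and to enter the ACQ estimate.

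The size and direction of any bias cannot be derived. The room for choice is 10 enrolled from about 27 to 107 patients per PCP (37% to 9%), before race and consent, if the plan's 69% and 97% rates apply. This does not show that bias will occur or that the trial is invalid. In a pilot whose first goal is feasibility, it calls for an inexpensive improvement. The conflict over who collects the phone ACQ6 also holds, as a separate and minor correction.

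**What to change.** 1. For each PCP, complete review of the administrator's list, with exclusions logged by reason, and as far as practicable the clinician contact, before that PCP's allocation is disclosed and training or control instruction starts. If this order is already intended, one sentence saying so closes most of the gap.
2. For patients identified later, use the administrator's query and allow PCP exclusion only for a logged reason.
3. Give Patient Recruitment and the DSMP the same wording, keeping the patient's agreement to be called.
4. Report the numbers listed, excluded (with reasons), contacted and consented by arm, with flyer recruits shown separately.
5. Separately, reconcile the Survey Administration table with its text and with Patient data collection, so that only the blinded RA collects the phone ACQ6.

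**Cost.** The sample stays at 80 and no visit is added. Review and contact are front-loaded, for up to about 160 asthma patients per PCP on the plan's figures. Some agreements will be older by the time of the call, and BREATHE training starts somewhat later. An exclusion log is needed. The DSMP report already covers enrollment by condition, so the added reporting is mainly the listed, excluded and contacted counts by arm. The Project Manager is lost as back-up caller.
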